10.2 Secondary study parameter(s)

The FiO₂ administer during the three different periods of the study is tested a repeated measurement ANOVA. Additional oxygen is only exactable when it results in a significant improvement in the stability of the SpO₂.

Manual FiO_2 changes are compared, and data is analysed to check for the reason of manual intervention during the automated FiO_2 period. Periods when the algorithm is turned off are reported, both in length, total period and average duration per period and total number of times that the algorithm was stopped. Normally the algorithm turns of when there are problems with either the SpO₂ measurement or the ventilation.

10.3 Other study parameters

All other parameters listed in Table 2 will be assessed for significant changes over time with repeated measurement ANOVA. Because the changes that are made to the ventilation can influence the need for additional oxygen, changes made to any relevant parameters will be described in the analysis. But the results cannot be corrected based on the changes. Cerebral saturation will be analysed if there is a significant improvement during the period of automated FiO₂ control.

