All modes use the flow sensor and ensure that ventilation occurs with adequate volume. Alarms are set to ensure that the clinical staff is warned when changes occur, and the PRICO algorithm is disabled when the alarm is triggered. Frequent apnea's can influence the results, but should be handled by the apnea back-up function. This function ensures adequate ventilation even during apnea's. Another variable during all ventilation modes is the amount of leak. Due to the un-cuffed tubes that are used in neonatology this is even the case in intubated patients. The amount of leak will be reported and analysed to ensure that there is no significant change between the different periods.

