4.4 Sample size calculation

The sample size calculation is based on the area under the curve for the SpO_2 . Giving a value that has a unit of [% SpO_2 *min]. A value of 30 can be reached by a SpO_2 of 30% outside of the target during 1 minute, or 30 minutes a SpO_2 that is 1% outside of the target. Values are normalized per hour.

During the animal trial conducted with this algorithm a reduction in the average of the area under the curve was found from 21 to 3 [%SpO₂*min per hour], with a standard deviation of 30 [%SpO₂*min per hour]. We accepted a significance level of 5% and a power of 80%. Because of the study design, each patient is its own control. Because of that only 22 patients are needed (Stata, StataCorp LP, USA). Because we want to show that the algorithm works in all 3 strata of ventilation we need three groups of 22 patients, and we expect a 10% dropout rate due to withdrawal or improvement in ventilation up to the point that additional oxygen is no longer needed, resulting in a total sample size of 72 patients.

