8.1.3 Other study parameters (if applicable)

All ventilation and patient monitor parameters are recorded (see table 2). Ventilation support is checked for changes due to pressure, volume and timing changes, because these can influence the need for oxygen. Because the interaction is too complex to adjust for, it will be mentioned in the analysis, but only in a descriptive manner.

When the patients cerebral oxygenation is monitored with NIRS this data will be recorded as well and analysed to see if automated control of the FiO_2 will lead to an improved stability (lower SD) of the cerebral oxygenation.

Table 2: Measured parameters	during the study
------------------------------	------------------

PARAMETER	ABBREVIATION	SAMPLE RATE	DEVICE
Gestational age	GA	Ones	
Age	Age	Ones	
Birthweight	Bw	Ones	
Weight	Weight	Ones	
Gender	Gender	Ones	
Ventilation Measurements			
Oxygen saturation	SpO ₂	1 Hz	Fabian HFO
Pulse rate	Pulse	1 Hz	Fabian HFO
Fraction of inspired oxygen	FiO ₂	1 Hz	Fabian HFO
Inspired tidal volume	Vti	1 Hz	Fabian HFO
Expired tidal volume	Vte	1 Hz	Fabian HFO
Air leak	%Leak	1 Hz	Fabian HFO
Positive end expiratory pressure	PEEP	1 Hz	Fabian HFO
Peak inspiratory pressure	PIP	1 Hz	Fabian HFO
Respiratory rate	RR	1 Hz	Fabian HFO
Inspiratory time	Ti	1 Hz	Fabian HFO
Expiratory time	Те	1 Hz	Fabian HFO
End tidal carbon dioxide	EtCO ₂	1 Hz	Fabian HFO
Patient monitoring			
Oxygen saturation	SpO2		M540
Pulse rate	Pulse		M540
Respiratory rate	RR		M540
Non-invasive blood pressure	Nbp		M540
Heart rate (if available)	ECG		M540
Extra during HFO ventilation			
Mean airway pressure (HFO only)	Pmean	1 Hz	Fabian HFO
Pressure amplitude (HFO only)	Pamp	1 Hz	Fabian HFO

Additional parameters if available			
Cerebral regional oxygen saturation	cSrO2	1/5 Hz	Invos
Hero Score (Heart rate variability)	Hero	1 Hour	Hero
Transcutaneous Oxygen	TcO2	1 Hz	Sentec
Transcutaneous CO2	TcCO2	1 Hz	Sentec

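### The leak check treats a non-significant test as proof that the periods are alike, and section 10.3 significance-tests parameters whose changes section 8.1.3 says are only described (minor)

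*Protocol*

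**What the plan says.** Three places in the protocol bear on this.

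- **Section 3 (Study design)**, on air leak: "The amount of leak will be reported and analysed to ensure that there is no significant change between the different periods". No margin, interval or significance level is given, and it is not said whether the analysis is by stratum or pooled.
- **Section 8.1.3 (Other study parameters)**, on pressure, volume and timing changes. These are held to interact with oxygen need in too complex a way for adjustment, so "it will be mentioned in the analysis, but only in a descriptive manner".
- **Section 10.3 (Other study parameters)**: "All other parameters listed in Table 2 will be assessed for significant changes over time with repeated measurement ANOVA". It goes on to say that relevant ventilation changes will be described and that the results cannot be corrected for them. It also looks for a significant improvement in cerebral saturation.

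The only significance level in the protocol is in section 4.4, for the sample size of the main parameter: "We accepted a significance level of 5% and a power of 80"%. The same section plans three ventilation strata of 22 infants.

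**The concern.** The first problem is the logic of the leak check. A test that fails to reject does not show that periods are alike; it may only reflect few infants. This matters more here than in a randomised trial. The order is fixed (manual, automated, manual), nobody is blinded, and the protocol rules out correcting the result for ventilation changes. A shift in leak confined to the automated block would be mixed up with the effect of the controller, and the return to manual control would not expose it. The leak check is one of the few safeguards, and as worded, low power looks like reassurance.

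The second problem is that section 10.3 attaches a significance verdict to every remaining Table 2 parameter, while section 8.1.3 promises description only for the ventilation parameters among them. With many verdicts and no stated error control, a chance change could be offered as an explanation of the SpO₂ result.

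**Working it through.** **Inputs from section 4.4.** The stated figures are "a reduction in the average of the area under the curve was found from 21 to 3" (a difference of 18), "with a standard deviation of 30", 5% and 80%. Reading the SD as that of the paired difference and the test as two-sided:

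n = (SD × (z₀.₉₇₅ + z₀.₈₀) / difference)² = (30 × (1.960 + 0.842) / 18)² = 21.8, so 22.

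This reproduces the protocol's 22. I therefore use 22 infants per stratum and 3 × 22 = 66 pooled.

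**Step 1: what the leak test misses.** Assumptions: three-period repeated measures ANOVA at 5%, equal correlation between periods, and a true shift in the automated period only. The shift is d times the SD of the within-infant difference between two periods.

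- That SD is √2 × σ, where σ is the residual SD, so the shift is d × √2 × σ.
- The squared deviations of the three period means from their average sum to (2/3) × shift².
- Noncentrality: λ = n × (2/3) × 2d² = (4/3) × n × d².
- Degrees of freedom: 2 and 2(n − 1).

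| n | d | λ | power | missed |
|---|---|---|---|---|
| 22 | 0.4 | 4.69 | 45% | 55% |
| 22 | 0.5 | 7.33 | 64% | 36% |
| 66 | 0.4 | 14.08 | 92% | 8% |
| 66 | 0.5 | 22.0 | 99% | 1% |

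A paired comparison of the automated period with one manual period agrees closely: with 22 infants it misses 0.5 SD 39% of the time and 0.3 SD 73% of the time. The 95% interval for that difference has half-width t₀.₉₇₅/√n: 2.080/√22 = 0.44 SD in a stratum and 1.997/√66 = 0.25 SD pooled. The interval shows what a bare non-significant result hides.

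**Step 2: how many other parameters are tested.** Counted from Table 2, leaving out SpO₂, FiO₂ and the five items recorded once:

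- always recorded: 10 ventilator parameters, plus monitor pulse rate, respiratory rate and blood pressure = 13;
- conditional: heart rate from ECG (1), HFO only (2), additional if available (4) = 7;
- maximum: 20.

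**Step 3: chance of at least one false change.** Assumptions: 5% per test, no true change in any parameter, one analysis. If independent, the chance is 1 − 0.95ᵏ: 48.7% for k = 13, 51.2% for k = 14 and 64.2% for k = 20. The expected number of false changes is 0.05k, or 0.65 to 1.0.

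For equally correlated parameters, simulation (n = 22, three periods, 4,000 runs each) gave:

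| correlation | 13 tests | 20 tests |
|---|---|---|
| 0.3 | 43% | 56% |
| 0.5 | 36% | 43% |
| 0.7 | 25% | 31% |
| 0.9 | 15% | 17% |

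**The case against.** The strongest reply is that little hangs on these tests. They sit in a third tier, below the main and secondary parameters; no success criterion uses them; and the primary comparison in section 10.1 is computed whatever they show. All of that stands, and they do not inflate the primary error rate. Error control for such parameters is also commonly left to a statistical analysis plan, which is not at hand, so its absence is not counted here.

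It can also be said that sections 8.1.3 and 10.3 agree on use: both describe ventilation changes and neither adjusts for them. That is right about use, but the opening sentence of 10.3 still asks for a significance test on the same parameters. Leak values will be reported as well as tested, and with 66 infants pooled the test is sensitive to shifts of 0.4 SD or more. That stands too, but pooling is not stated, and the strata were formed because ventilation efficiency is expected to differ between them.

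A reader might infer more than the text supports:

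- **That a false change is likely.** This needs about 14 or more nearly independent tests. Several Table 2 signals overlap (pulse and heart rate, respiratory rate twice, the tidal volumes and leak, the timing parameters), and seven of the 20 are conditional.
- **That 5% is the stated level for section 10.3.** It is carried over from section 4.4.
- **That the protocol has no ranking.** It has three tiers; what it lacks is the word exploratory and a formal testing order.
- **That many false benefit claims are in prospect.** Cerebral saturation is the only one of these parameters with a named improvement.
- **That pressure and timing are also declared comparable by non-significance.** The wording in section 3 covers leak alone.
- **That the tests are repeated in each stratum.** Section 10.3 does not say so.

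**Conclusion.** The concern holds in a limited form, and is minor. The leak rule in section 3 infers comparability from non-significance, which is unsound at any sample size without a margin or interval. In practice it is weak at stratum level (a 0.5 SD shift missed about one time in three) and much less so if pooled. The testing in section 10.3 fits badly with the descriptive role in section 8.1.3 and carries a substantial, though not always better-than-even, chance of a spurious change. The sizes rest on an assumed 5% level, equal correlation between periods for the miss rates, and a range of assumed correlations between parameters. The harm would be in how the SpO₂ result is explained, not in whether the primary test is valid.

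**What to change.** In section 3, replace the aim of ensuring no significant change in leak with: the automated-minus-manual difference in leak is reported with its 95% confidence interval, by stratum and overall, and comparability is judged from the interval.

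In section 10.3, replace the first sentence with: the other time-varying Table 2 parameters are descriptive; for each, differences between periods are reported with 95% confidence intervals and without significance claims. This brings 10.3 into line with 8.1.3. If the sponsor wants a formal claim on the stability of cerebral oxygenation, it can be named as a single secondary test after the primary.

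The cost is two sentences, with no new data or infants. The small downside is giving up statements of significant change on individual third-tier parameters.

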An observational study conducted on our Neonatal Intensive Care Unit (NICU) has shown that infants on average spend only 54% of the time within the SpO_2 limits and 71 adjustments to the FiO₂ are made each day.

An automated controller (PRICO) has been developed that adjusts the FiO₂ based on the SpO₂. A study in a preterm lamb model has shown the effectiveness of this closed loop controller: less periods of desaturation and hyperoxia were demonstrated.

Objective: To test the safety and feasibility of a closed loop controller of the FiO_2 based on the measured SpO_2 in a NICU setting.

Study design: Neonates that are included will start with an 8 hour block of manual adjustment of the FiO₂. After completion of this block they will be switched to the automated control of the FiO2 for another 8 hours. After that they are switched back for another 8 hours of manual control, which is used to correct for any changes of the state of the neonate during the trial. For each ventilation type (high frequency , invasive and non-invasive) 24 patients will be included.

Study population: Neonates admitted to the NICU in the Erasmus MC, Rotterdam and Máxima Medical Centre, Veldhoven that are receiving respiratory support and a FiO_2 of more than 21%.

Intervention (if applicable): Automated control of the FiO₂ based on the measured SpO₂ during 8 hours.

Main study parameters/endpoints: The main parameter during the study is the time the SpO₂ spend within the target range. Secondary outcomes are the number of hyper and hypoxic events, average maximum and minimum SpO₂ during these events, number of FiO₂ adjustments (manual and automated) and cerebral oxygen saturation.

Nature and extent of the burden and risks associated with participation, benefit and group relatedness: There is no burden to the patient, and the risk is minimal. The same patient monitoring is used during the study as during routine care. The closed loop

algorithm is implemented in to the Acutronic Fabian HFO ventilator, so that no additional equipment is needed at the bedside.

The controller is designed so that it checks the input signals, the validity of the pulse oximetry and the quality of the ventilation. If any of the checked parameters is not within the specified limits the controller will not adjust the FiO_2 and give an alarm.

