2. OBJECTIVES

Primary Objective: To test the safety and feasibility of a closed loop controller of the FiO_2 based on the measured SpO_2 in a NICU setting. This is determined by the time spend within the SpO_2 target range, and the number of times the SpO_2 was above and below the target.

Secondary Objective(s):

Track the usage of the fraction of inspired oxygen (FiO₂) during the periods. A higher oxygen use is only acceptable when it results in an improvement of the time spend within the oxygen saturation target range without a rise in hyperoxia. In all other cases a lower FiO_2 is preferred.

The respiratory support is analysed, to see if any changes were made to the ventilation settings. Changes to the pressure or timing can influence the need for additional oxygen.

Reduction in manual FiO_2 adjustments. Although the FiO_2 is adjusted automatically, it is still possible to adjust the FiO_2 by hand. This can be done on clinical indication. For example before an alteration to the respiratory support is made, before suctioning, or before respiratory support is halted for another reason.

[figure not shown]
When the infants are monitored with near infrared spectroscopy (NIRS) to monitor their cerebral oxygenation, this data will be analysed in order to see if automated oxygen control improves the stability of their cerebral oxygenation.

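### The last sentence of 10.3, read literally, makes the analysis of cerebral saturation depend on a significant improvement, in conflict with the rest of 10.3, section 2, 8.1.3 and the Summary

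*Protocol*

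**What the plan says.** The protocol speaks of the cerebral analysis in five places.

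- **Section 10.3, last sentence:** "Cerebral saturation will be analysed if there is a significant improvement" in the automated period. This is the only sentence in section 10 that names cerebral saturation.
- **Section 10.3, first sentence:** "All other parameters listed in Table 2 will be assessed for significant changes over time with repeated measurement ANOVA". Table 2 lists "Cerebral regional oxygen saturation" among the additional parameters recorded if available.
- **Section 8.1.3:** when NIRS is in use, the data are recorded and "analysed to see if automated control of the FiO_2 will lead to an improved stability (lower SD) of the cerebral oxygenation".
- **Section 2:** for infants monitored with NIRS, "this data will be analysed in order to see if automated oxygen control improves the stability of their cerebral oxygenation".
- **Summary, main study parameters/endpoints:** cerebral oxygen saturation closes the list of secondary outcomes, with no condition attached.

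**The concern.** Whether an outcome is analysed should not depend on how the results turn out. The last sentence of 10.3, as worded, sets such a condition, and the condition points one way: it is met by an improvement and not by a null result or a worsening. If it were followed, the cerebral data would be examined mainly in the circumstances where the controller looks good.

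The context gives this some weight. Section 1 names possible harm of hyperoxia to the developing brain as part of the rationale. Section 6.3 says the algorithm has not yet been tested in a clinical trial. Section 13.2 gives overshoot as the biggest residual risk. Cerebral saturation is the only measure of brain oxygenation in Table 2, so it is the one place where an effect on the brain, in either direction, could be seen.

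**Working it through.** No arithmetic applies. The check is to set the statements side by side and see what an analyst could do with each.

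**Step 1: the condition in each place.**

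- Summary: none stated.
- Section 2: NIRS in use.
- Section 8.1.3: NIRS in use.
- Section 10.3, first sentence: the parameter is in Table 2 and is not already dealt with. Sections 10.1 and 10.2 deal with SpO₂, FiO₂, manual changes and controller stops, so cerebral saturation falls under this sentence.
- Section 10.3, last sentence: a significant improvement in the automated period.

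Four statements do not depend on the results and one does. The odd one out is in the analysis section and is the most specific to this parameter.

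**Step 2: possible readings of the last sentence of 10.3.**

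1. *The analysis is done to find out whether there is an improvement.* This needs a few missing words supplied. It agrees with sections 2 and 8.1.3, and nothing is left out.
2. *The analysis is done if cerebral saturation itself has improved significantly.* This is circular, because significance cannot be known before the analysis. It could only work as a filter on what is reported, and the sentence does not mention reporting.
3. *The analysis is done if SpO₂ control has improved significantly.* An analyst can carry this out: run 10.1 first, then decide whether to open the NIRS data. It is not far-fetched, since 8.1.2 and 10.2 both speak of a significant improvement with reference to SpO₂. Under it, the cerebral data are left out when the controller does not help.

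The sentence does not say what must improve, so it does not choose between these readings.

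**Step 3: does the first sentence of 10.3 settle it?** Only in part. It commits to testing cerebral saturation for change over time, in either direction. But a reader can take the specific sentence that follows as an exception to the general one; otherwise it would add little. The general sentence also does not say which summary of each parameter is tested, whereas 8.1.3 asks about stability, measured by the SD within a period. The planned stability analysis is therefore not clearly secured by it.

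**The case against.** The strongest answer is that this is loose English. Sections 2 and 8.1.3 describe the same analysis as one done to see whether stability improves, and 10.3 most likely means the same. Nearby text has similar slips; the first sentence of 10.2, for instance, lacks a word before the name of the test. The first sentence of 10.3 independently commits to a test of every remaining Table 2 parameter. Cerebral NIRS is also opportunistic: it enters neither the sample size in 4.4 nor the halting criteria in 8.7.

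Most of this stands. A reader might infer that a null or harmful cerebral result would not be analysed. The documents do not support that, for three reasons: the first sentence of 10.3 tests for change in both directions, sections 2 and 8.1.3 commit to the analysis whenever NIRS is in use, and a trigger on the cerebral result itself is circular.

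A reader might also want to put a figure on selective reporting, such as the inflation of an apparent benefit. That would require the circular reading and a number of infants with NIRS, which the protocol does not give.

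The answer does not remove the conflict. The likely intent has to be reconstructed from other sections, the protocol sets no order of precedence among them, and the gate on SpO₂ control remains workable as the text stands.

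**Conclusion.** The point holds as a contradiction and an ambiguity in the analysis text. The literal wording of the last sentence of 10.3 is outcome-dependent and disagrees with the first sentence of the same section, with section 2, with 8.1.3 and with the Summary. A slip of wording is the likely explanation, and intent to withhold unfavourable results is not shown. The practical risk is that an analyst follows the text as a gate on SpO₂ control and leaves out the cerebral data in exactly the case where the controller gave no benefit.

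No numerical size can be derived from the protocol. Since the parameter is recorded only if available and is not primary, the severity is minor to moderate. This rests on the protocol alone; a separate statistical analysis plan might already state the analysis properly, but the protocol sentence would still need to agree with it.

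**What to change.** Replace the last sentence of 10.3 with wording such as: *In all infants with NIRS, the SD of cerebral saturation per period will be compared between the automated and manual periods and reported whatever the direction or significance of this or any other result.*

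This keeps the measure that 8.1.3 already names and removes the condition. In the same edit, the label can be made consistent, since the Summary calls cerebral saturation a secondary outcome while 8.1.3 and 10.3 place it among the other parameters.

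The cost is one sentence. No additional data, patients or measurements are needed.

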10.4 Interim analysis (if applicable)

Not applicable

11.ETHICAL CONSIDERATIONS

